9.4.6.1 CATEGORICAL ENDPOINTS

Frequency and percentages for each response Yes/No for categorical endpoints will be presented separately by visit for each treatment arm. Estimates of the difference between treatments (imsidolimab – placebo) will be presented along with exact 90% CIs. Treatment arms will be compared using an exact test.

9.4.6.2 CONTINUOUS ENDPOINTS

Summary statistics will be provided by visit and treatment arm. A by-subject listing will be presented for each assessment, by visit.

9.4.7 ANALYSIS OF THE EXPLORATORY EFFICACY ENDPOINTS

Following are the exploratory efficacy endpoints:

- Two-point decrease from Baseline in Facial IGA at each visit
- Change from Baseline in Truncal PGA for chest at each visit
- Change from Baseline in Truncal PGA for neck at each visit
- Change from Baseline in Truncal PGA for back at each visit
- Proportion of subjects achieving a Truncal PGA for chest of clear (0) or almost clear (1) with at least a 2-grade decrease from Baseline at each visit
- Proportion of subjects achieving a Truncal PGA for neck of clear (0) or almost clear (1) with at least a 2-grade decrease from Baseline at each visit
- Proportion of subjects achieving a Truncal PGA for back of clear (0) or almost clear (1) with at least a 2-grade decrease from Baseline at each visit
- Proportion of subjects in each response category for the SSQ at each visit
- Proportion of subjects in each response category for the SSRS at Week 12 and Week 20
- Change from Baseline in lesion counts based on blinded photographic assessment at each visit

Efficacy and Safety of Imsidolimab in Subjects with Acne Vulgaris
Protocol ANB019-209

Version 1.0
11 February 2021

Methods for analyzing the above categorical and continuous efficacy endpoints will mirror the methods described in [Section 9.4.6.1](#) and [9.4.6.2](#), respectively.

9.4.8 SAFETY ANALYSES

Following are the primary safety and tolerability endpoints:

- Assessment of AEs, SAEs, and AEs leading to treatment discontinuation and study withdrawal.
- Vital signs.
- 12-Lead ECG.
- Clinical safety laboratory tests (hematology, biochemistry, and urinalysis).

All safety analyses will be performed on the safety analysis set.

9.4.8.1 ADVERSE EVENTS AND SERIOUS ADVERSE EVENTS

A TEAE is defined as:

- A new event that occurs during or after first dose of study treatment or,
- Any event present at Baseline that worsens in either intensity or frequency after first dose of study treatment.

Adverse events will be coded using the MedDRA and only TEAEs will be summarized. Number of events and percentage will be tabulated by preferred term (PT) and primary system organ class (SOC). Multiple occurrences of an AE for a subject will only be counted once per primary SOC and PT. Percentages will be determined relative to the subjects in the safety analysis set for the given treatment arm.

If the intensity or seriousness of the AE changes, the overall intensity or seriousness will be the maximum intensity or seriousness of the multiple occurrences. The TEAEs, SAEs, TEAEs leading to treatment discontinuation, and TEAEs leading to withdrawal of subject will be tabulated for each treatment arm.

All AE data will be listed for each subject.

Summaries over SOC and PT of TEAEs, TEAEs leading to death, SAEs, and TEAEs that led to discontinuation from the study or study treatment will be presented by treatment. Summaries will also be presented by relatedness to the study treatment and the severity of the TEAE.

9.4.8.2 12-LEAD ELECTROCARDIOGRAM, VITAL SIGNS, AND CLINICAL SAFETY LABORATORY TESTS

Summaries and listings of data for vital signs and safety laboratory tests result (hematology, biochemistry, and urinalysis) will be presented. Appropriate descriptive statistics will be summarized for the observed value at each scheduled assessment and for the corresponding change from Baseline.

For hematology and biochemistry tests, listings of subject data will also flag any abnormal or out-of-range values. Clinically significant changes in the laboratory test parameters will be summarized and listed. Hematology and biochemistry data will be reported in System International units.

Descriptive statistics will be used to present the safety outcomes including, weight, BMI, 12-Lead ECG, vital signs, and clinical laboratory test results.

Change from Baseline will also be summarized for vital signs, and clinical laboratory tests results.

All ECG data results (normal/abnormal) will be summarized using frequency and percentage, and parameter values will be summarized descriptively. Clinically significant abnormalities will be presented in by-subject listings.

9.4.9 PHARMACOKINETIC ANALYSES

Limited imsidolimab PK parameter analysis will be evaluated by assessment of drug concentrations in serum. These drug concentrations will be listed and summarized for each sampling time point using appropriate descriptive statistics. The PK parameters will be summarized using appropriate descriptive statistics.

9.4.9.1 DERIVATION OF PHARMACOKINETIC PARAMETERS

Where possible, PK parameters will be derived using noncompartmental methods. The actual sampling times will be used in the PK parameter calculations. Further details of PK analysis, data handling, analysis procedures, and data reporting will be detailed in a separate analysis plan.

9.4.9.2 PHARMACOKINETIC CONCENTRATION DATA ANALYSIS

A subject listing of all concentration-time data following SC injections will be presented by subject and scheduled sample collection time.

Efficacy and Safety of Imsidolimab in Subjects with Acne Vulgaris
Protocol ANB019-209

Version 1.0
11 February 2021

Concentration data of imsidolimab will be summarized by day and nominal time point using the number of observations, arithmetic mean, SD, CV, minimum, median, maximum, and geometric mean.

Graphs for mean concentration-time data following SC administration will be presented. Individual subject concentration-time plots will also be presented.

Mean trough concentrations-time data will be graphically displayed for samples collected at the visits specified in the SoA ([Section 1.3](#)) to visually assess time to attainment of steady state. Time to steady state may also be explored by using inferential statistics, if deemed appropriate. Other presentations of data may be added at the discretion of the PK scientist, as appropriate, and will be described in detail in a separate analysis plan.

9.4.9.3 PHARMACOKINETIC PARAMETER DATA ANALYSIS

Where possible, PK parameters will be summarized using number of observations, arithmetic mean, SD, CV, minimum, median, maximum, geometric mean, and geometric CV, with the exception of time to maximum observed concentration (T_{max}), which should be reported with n, minimum, median, and maximum only.

Graphs of parameters may be added at the discretion of the PK scientist, as appropriate, and will be described in detail in a separate analysis plan.

9.4.9.4 POPULATION PHARMACOKINETICS ANALYSIS

Pharmacokinetic data from the study may also be used for population PK and PK/response analyses. The data may be combined with PK data from other imsidolimab studies, if needed, to conduct the population PK analysis. If done, a separate analysis plan will be prepared, and results will be reported separately from the Clinical Study Report (CSR).

9.4.9.5 IMMUNOGENICITY ANALYSES

Observed values for ADA levels/status will be listed by-subject and summarized with descriptive statistics based on the safety analysis set. If data permits, correlation will be analyzed between ADA levels, serum concentration, and safety and efficacy endpoints.

Frequency and percentage of ADA response will be presented and listed and correlated to safety and PK endpoints.

Efficacy and Safety of Imsidolimab in Subjects with Acne Vulgaris
Protocol ANB019-209

Version 1.0
11 February 2021

9.4.10 BIOMARKER ANALYSES

Tape strip samples will be collected from nonlesional and lesional skin according to the SoA ([Section 1.3](#)) to measure cutaneous biomarkers including but not limited to IL-36R, Th-17 cytokines such as IL-17A, and markers of neutrophils and dendritic cell infiltration.

The actual date and time of the sample collection will be recorded in the subject's eCRF. The details of tape strip collection, sample tube labeling, sample preparation, storage, and shipping procedures will be described in a separate Laboratory Manual.

The measurement of tape strips biomarkers may be performed by an additional third party (eg, a university Investigator) designated by AnaptysBio.

9.4.11 PLANNED INTERIM ANALYSIS

Interim analyses (IA) may be performed for assessment of all primary and secondary efficacy endpoints, and evaluation of all safety data available.

The rationale for these analyses is to assist in making decisions for potential future development of this treatment. No adjustments to the current protocol are planned as a result of the interim analyses; therefore, overall alpha in the analyses of the primary analysis is expected to be maintained at 0.10, two-sided.

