9 STATISTICAL CONSIDERATIONS

9.1 STATISTICAL HYPOTHESES

The primary analysis for this study is to compare the mean facial inflammatory lesion count for imsidolimab with placebo during the treatment period, at a two-sided alpha = 0.10 level. Any testing being performed for secondary or exploratory endpoints will be considered exploratory in nature based on a 2-sided alpha = 0.10

$H_0: \mu_{\text{imsidolimab}} - \mu_{\text{placebo}} = 0$ vs. $H_A: \mu_{\text{imsidolimab}} - \mu_{\text{placebo}} \neq 0$

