9.2 SAMPLE SIZE DETERMINATION

Approximately 120 subjects will be stratified based on facial IGA score at baseline (3 [moderate] versus 4 [severe]) and randomized in a 1:1:1 ratio to receive one of the following study treatments:

- Imsidolimab 400 mg on Day 1, 200 mg on Days 29 and 57
- Imsidolimab 200 mg on Day 1, 100 mg on Days 29 and 57
- Placebo on Days 1, 29, and 57

For this Phase 2 study, the sample size was chosen empirically. Assuming a total of 10% of subjects will discontinue prior to Week 12, there will be approximately 108 evaluable subjects (36 subjects in each arm) at the end of Week 12.

The study has 80% power to detect a between-group treatment difference of 6.1 lesions in the primary endpoint of mean change from baseline in the AN count at Week 12, using a 2-sided, equal-variance two-sample t-test at the $\alpha = 0.10$ level, with the assumption of a common standard deviation (SD) of 10.4 lesions. The assumption was based on Arazlo (tazarotene) acne Phase 3 Study Trial-301 results (Ararzlo 2019). Table 6 shows more information on power from a set of scenarios of variability and between-group mean differences.

Table 6: Power Exploration for Different Scenarios of Variability and Between-group Mean Differences

Common Standard Deviation (SD)	Between-group mean difference	Power (%)	
		1-sided test	2-sided test
8	3	62	48
	4	80	68
	5	92	84
	6	97	94
10	3	50	36

Efficacy and Safety of Imsidolimab in Subjects with Acne Vulgaris
Protocol ANB019-209

Version 1.0
11 February 2021

Common Standard Deviation (SD)	Between-group mean difference	Power (%)	
		1-sided test	2-sided test
	4	66	52
	5	80	68
	6	90	82
12	3	41	28
	4	55	41
	5	69	55
	6	80	68

Note: An equal variance two-sample t-test at alpha=0.10 is used for the power calculations.

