### 3.3 Hypothesis Testing

The primary analysis for this study is to compare the mean facial inflammatory lesion count for imsidolimab at each dose with placebo during the treatment period, at a two-sided alpha = 0.10 level. Any

testing being performed for secondary or exploratory endpoints will be considered exploratory in nature based on a 2-sided alpha = 0.10.

$$H_0: \mu_{imsidolimab} - \mu_{Placebo} = 0 \text{ vs. } H_A: \mu_{imsidolimab} - \mu_{Placebo} \neq 0$$

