### 3.4 Interim Analysis

A primary analysis, considered as the interim analysis of this study, will be performed when all randomized subjects have reached Week 12 or discontinued. The purpose of the primary analysis is to assist AnaptysBio executive management in making decisions for potential future development of this compound. No adjustments to the protocol are planned as a result of the primary analysis; as such, the type I error will not be adjusted in the primary analysis and is expected to be maintained at 0.10, two-sided.

Only data collected on or prior to the data cut-off date will be included in the primary analyses.

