### 7.5 Efficacy Analyses

The ITT Analysis Set will be used as the primary analysis set for all efficacy analyses. Per protocol analyses will be performed on the primary as well as the following secondary endpoints:

- Change from Baseline in facial inflammatory lesion counts at visits other than Week 12
- Change from Baseline in facial noninflammatory lesion counts at each visit
- Change from Baseline in total facial lesion (inflammatory and noninflammatory lesions) counts at each visit
- Change from Baseline in facial IGA at each visit
- Proportion of subjects achieving a facial IGA of clear (0) or almost clear (1) with at least a 2-grade decrease from Baseline at each visit

No adjustment for multiplicity will be made.

All statistical tests will be performed at the 10% level of significance unless otherwise stated. All confidence intervals (CIs) will be reported as 2-sided 90% CIs unless otherwise stated. Descriptive statistics will be provided for the continuous variables as number of subjects, mean, SD, standard error of the mean, first and third quartiles, minimum, and maximum. Descriptive summaries of continuous variables will be shown for baseline, change from baseline to endpoint, and percent change from baseline to endpoint. All data will be listed in data listings.

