#### 7.5.1 Primary Efficacy Analysis

The primary estimand, comprising four components, is defined as follows:

- a) The target population consists of patients with acne vulgaris that are eligible to be included in the clinical trial based on the inclusion/exclusion criteria in the protocol. The ITT Analysis Set will include all randomized subjects. For the analysis, treatment will be assigned based upon the treatment arm to which subjects were randomized regardless of which treatment they receive.
- b) The primary variable is the change from baseline in facial inflammatory lesion count of an individual subject at Week 12.
- c) To handle intercurrent events such as use of rescue medications, the hypothetical strategy for estimand will be used. Data collected following receipt of rescue medication (if any) will be considered missing in the analysis.
- d) The population-level summary measures will be the population mean differences in the primary variable between each dose of imidolimab and placebo at Week 12.

A MMRM model will be used with treatment, visit (Weeks 2, 4, 8, and 12), treatment by visit interaction, and facial IGA score at baseline (Grade 3 vs. 4) as categorical covariates and the baseline value of response as the only continuous covariate; only the visits up to and including week 12 are used. An unstructured correlation (UN) matrix will be used to model correlation within a subject; if convergence is an issue, a Toeplitz structure may be considered. Subjects with missing data at Week 12 due to early discontinuation will be included in the model.

The least squares (LS) mean and the standard error of this mean with the corresponding two-sided 90% CI will be provided for each treatment based on the model. The LS mean difference between treatments (imsidolimab – placebo), as well as the corresponding two-sided 90% CI will be provided based on the model. Summary statistics and the results of statistical testing in facial inflammatory lesion count at Week 12 will be tabulated. The LS mean change from baseline as well as differences between treatments in facial inflammatory lesion count will be plotted across post-baseline visits by treatment in separate plots.

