## **8.      CHANGES FROM METHODS PLANNED IN THE PROTOCOL**

The following exploratory analyses have been added:

- Change and percent change from Baseline in facial papule lesion counts at each visit
- Change and percent change from Baseline in facial pustule lesion counts at each visit
- Change and percent change from Baseline in facial nodule lesion counts at each visit
- Change from Baseline in overall Truncal PGA at each visit
- Proportion of subjects with at least 1-point decrease from Baseline in facial IGA at each visit

- Proportion of subjects with at least 1-point decrease from Baseline in overall Truncal PGA at each visit for subjects with Baseline overall Truncal PGA score of at least 1
- Proportion of subjects with at least 2-point decrease from Baseline in overall Truncal PGA at each visit for subjects with Baseline overall Truncal PGA score of at least 2
- Proportion of subjects achieving an overall Truncal PGA of clear (0) or almost clear (1) with at least a 2-grade decrease from Baseline at each visit for subjects with Baseline overall Truncal PGA score of at least 2
- Proportion of subjects achieving improvement (“Much better” or “Very much better”) according to the PGI-C at each visit
- Proportion of subjects achieving improvement (“A little better”, “Much better” or “Very much better”) according to the PGI-C at each visit
- Proportion of subjects achieving “Mild” or “Clear skin” according to the PGI-S at each visit
- Change from Baseline in PGI-S at each visit
- Proportion of subjects achieving “slightly satisfied”, “somewhat satisfied”, or “extremely satisfied” according to the SSQ at each visit
- Proportion of subjects achieving “slightly satisfied”, “somewhat satisfied”, or “extremely satisfied” according to the SSRS at Week 12 and Week 20
- Proportion of subjects achieving a DLQI of 0 or 1 at each visit for subjects with Baseline DLQI of at least 2
- Change from Baseline in PAS score based on blinded photographic assessment at each visit
- Change from Baseline in erythema score based on blinded photographic assessment at each visit

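### Does Protocol 9.4.11 misstate the error rate by calling 0.10 the overall alpha when two doses are each tested against placebo without adjustment?

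*Protocol*

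**What the plan says.** Protocol 9.4.11 allows interim analyses to guide later development. It says they will cause no change to the protocol and infers that "overall alpha in the analyses of the primary analysis is expected to be maintained at 0.10, two-sided".

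Protocol 9.1 states a single hypothesis, to "compare the mean facial inflammatory lesion count for imsidolimab with placebo during the treatment period, at a two-sided alpha = 0.10 level", without separating the doses. Protocol 9.2 then says: "The study has 80% power to detect a between-group treatment difference of 6.1 lesions in the primary endpoint", with 36 evaluable subjects per arm, a common SD of 10.4 lesions and a two-sided 0.10 t-test.

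The SAP is more specific. Section 3.3 sets the primary analysis to "compare the mean facial inflammatory lesion count for imsidolimab at each dose with placebo during the treatment period", with two-sided 0.10 in the same sentence. Section 3.4 reduces the interim analysis to one look, the primary analysis itself, taken when every randomized subject has reached Week 12 or discontinued. It adds: "as such, the type I error will not be adjusted in the primary analysis and is expected to be maintained at 0.10, two-sided". Section 7.5 says "No adjustment for multiplicity will be made", and item (d) of the estimand in 7.5.1 targets "the population mean differences in the primary variable between each dose of imidolimab and placebo at Week 12".

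Section 8, on departures from the protocol, opens with "The following exploratory analyses have been added" and lists nothing on this point.

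**The concern.** The word *overall* usually signals control across everything that counts as primary. Here the primary analysis contains two tests that share a placebo arm, each spends the full 0.10, and no passage ranks the doses, orders the tests or splits alpha. On that reading the protocol's one overall error rate is too low. SAP 3.4 drops the word but does not itself say that 0.10 is per dose, and SAP section 8 does not reconcile the two documents.

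The Week 12 results go to the sponsor's executive management to inform development decisions. A reader who took *overall* to span both doses would put the chance of a false favourable result on some dose at 0.05 (half of 0.10), when it is higher if neither regimen works.

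**Working it through.** **Inputs.** From Protocol 9.2 and SAP 3.5: 1:1:1 allocation, 120 × 0.90 = 108 evaluable, so 36 per arm; difference 6.1 lesions; SD 10.4; two-sided 0.10. From SAP 3.3, 7.5 and 7.5.1(d): two dose-placebo comparisons, unadjusted. Derived, not stated in the documents: the correlation between the two comparisons is (1/36) / (1/36 + 1/36) = 0.5.

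**1. Reproduce the stated power.** The standard error of a difference is 10.4 × √(2/36) = 2.451, and 6.1 / 2.451 = 2.489.
- Normal approximation: Φ(2.489 − 1.645) = 0.801.
- Noncentral t on 70 df: 0.794.

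Both agree with the stated 80%. Pooling the doses (72 against 36) would give 0.887, which does not. The sample size therefore already treats the primary test as one dose against placebo at the full 0.10.

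**2. Interim looks.** SAP 3.4 has one look, on complete Week 12 data, and the primary model in SAP 7.5.1 uses visits only up to Week 12. There is no earlier test of accumating data through which error could build up. For each dose comparison the level stays 0.10.

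**3. Across the two doses, if neither works.** With c = 1.645 and a bivariate normal with correlation 0.5:

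P(at least one rejection) = 1 − P(|Z₁| < c and |Z₂| < c) = 0.1755.

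With a pooled variance on 105 df it is 0.1751, and P(both rejected) = 0.20 − 0.1751 = 0.0249. Simulations gave 0.174 to 0.175. The rate would be 1 − 0.90² = 0.19 if the tests were independent, and it cannot exceed 0.20.

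**4. Direction.** P(at least one false result favouring imsidolimab) = 0.088, against 0.05 for one comparison. If exactly one dose works, the error for the other returns to 0.10 (0.05 in the favourable direction).

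**5. Sensitivity to the correlation.** Correlations of 0.4 to 0.6 give 0.181 to 0.169. Assumed evaluable numbers of 38/36/34 (placebo last) give a correlation of 0.521 and a rate of 0.174; 34/36/38 give 0.479 and 0.177.

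**6. What control at 0.10 across both doses would imply.** A single-step two-comparison (Dunnett) test needs a critical value of 1.936 on 105 df, or two-sided 0.0555 per comparison. Power at 6.1 lesions would then be 70.6%, or 68.9% with Bonferroni at 0.05. Neither is the stated 80%, so the design figures fit 0.10 per comparison and not 0.10 across both.

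**7. The passages together.** Protocol 9.4.11 gives one reason for its conclusion, that interim results will not alter the protocol, and that reason supports a statement about looks only. Protocol 9.4.1 leaves analysis details to the SAP. SAP 3.3 puts the level and the phrase on each dose in one sentence, 3.4 follows directly and speaks again only of the interim look, and 7.5 disclaims adjustment.

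**The case for a change.** The strongest case for a change is that disclosing the lack of adjustment does not disclose the error rate that results, and that the only rate labelled *overall* is 0.10. Two short additions to the SAP would close the gap at almost no cost. The stated 80% power and a 0.10 rate across both doses also cannot both hold under a single-step test.

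The arithmetic stands, and so does the point that *overall* lacks a qualifier. The rest carries less weight:

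- **The clash with 80% power.** This arises only if the sentence promised control across doses, which it does not. The power calculation is evidence that 0.10 was meant per comparison.
- **The silence of SAP section 8.** Protocol 9.2 already powers one pairwise comparison, and Protocol 9.4.5 fits treatment arm as a fixed effect. Two dose contrasts are arguably the protocol's own method spelled out, not a departure that section 8 should list.
- **The effect on a development decision.** The 0.088 matters most if success on either dose were enough to proceed. Neither document states such a rule. Protocol 4.3 presents the lower regimen as a way to study dose dependence, at an exposure expected to fall below the exposure-response curve. It is not presented as a second chance of success.
- **Cost.** A SAP note would be cheap. A protocol amendment would need the approvals described in Protocol 10.2.2, for a sentence that is correct in its own context.

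**Conclusion.** The concern does not hold as an error in the plan. In Protocol 9.4.11 the 0.10 is right for interim looks and for each dose comparison, and the SAP says openly that the two comparisons are not adjusted. That is a reasonable trade in a Phase 2 trial of this size: adjustment would cut power at 6.1 lesions from about 80% to about 70%.

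The consequence of that choice is worth knowing when the results are read. If neither regimen works, the chance of some false rejection is about 0.175, and of one favouring imsidolimab about 0.088. These figures assume 36 evaluable subjects per arm, a common variance and a correlation of 0.5 from equal allocation; over the correlations examined the 0.175 stays between 0.169 and 0.181. Anyone can derive them from what the plan already states.

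Qualifying the word would be a courtesy to readers if the SAP were reopened for another reason. It would alter no test, level, estimate, confidence interval or p-value, so no change is called for.
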